**Clinically indicated standard of care procedure/s:**

ERCP will be performed with cannulation of the bile duct and cholangiogram to identify any biliary stones. If stones are identified, they will be removed with conventional methods including sphincterotomy, sphincteroplasty, balloon extraction, basket retrieval, and/or lithotripsy. An occlusion cholangiogram will be performed to confirm duct clearance (usually performed by inflating the catheter balloon at the proximal common hepatic duct near the hilum and then pulling the balloon through the bile duct and into the duodenum. Then, based on clinical decision and inclusion criteria, the cholangioscope (Spyglass) will be inserted through the channel of the endoscope and into the bile duct. Any residual stones will be documented followed by further treatment as indicated e.g. stone extraction, lithotripsy, stent placement, etc.

All patients with suspected cholechodoliathiasis potentially meeting the Inclusion criteria will be enrolled in the study. This is the reason for taking the consent before hand when the patient is not sedated. However if on clinical judgment during the procedure, the physician decides not to perform the POC then the subject will be deemed as screen failure and will not be counted towards the final results of the study.

**Research procedures:**

1. Document the number of subjects who did and did not have any missed stones as identified by SpyGlass.
2. Document the number of stones missed if there were any.
3. Document clinical management after finding a stone.(eg: balloon sweep, lithotripsy, stent placement, etc.)
4. Follow-up contact with the participant  $\approx$ 3 months after the ERCP procedure if he/she is enrolled and had undergone cholangioscopy with Spyglass to document any recurrent stones/procedures/interventions.
5. Medical history will be obtained either directly from the patient or from the patient medical records which may also include questions about prior problems with medications used for sedation or other unusual medication reactions.
6. De-identified ERCP, endoscopic, EUS and SpyGlass images and/or video recordings may be collected for review, analysis, presentations and publications.

## 12. STATISTICAL ANALYSIS

- *Describe how your data will be used to test the hypotheses.*
- *State clearly what variables will be tested and what statistical tests will be used.*
- *Include sample size calculations.*
- *If this is a pilot study, state which variables will be examined for hypothesis generation in later studies.*

### **Statistical Considerations:**

#### **Specific Aims:**

1. To estimate the proportion of subjects with missed stones on conventional ERCP.
2. To identify changes in management after finding a stone on POC.

#### **Endpoint Variables:**

1. Missed stones: Patients will be considered to have missed stones on conventional ERCP, if, after ERCP, one or more stones are seen with POC.
2. Change in management: any maneuver or combination of maneuvers performed after a missed stone (e.g. balloon extraction of stone, lithotripsy of stone, stent placement, etc.)
3. Recurrent stones within 3 months after POC, and documentation of cholecystectomy as applicable.

#### **Statistical Methods:**

1. The proportion of subjects with missed stones will be estimated, along with the associated exact 95% binomial confidence interval.
2. Change in management will be described by calculating frequencies and percentages for each maneuver performed. This analysis will be restricted to subjects with missed stones.
3. The proportion of subjects with recurrent stones will be estimated, along with the associated exact 95% binomial confidence interval.

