## 2. BRIEF SUMMARY OF RESEARCH

- *The summary should be written in language intelligible to a moderately educated, non-scientific layperson.*
- *It should contain a clear statement of the rationale and hypothesis of your study, a concise description of the methodology, with an emphasis on what will happen to the subjects, and a discussion of the results.*
- *This section should be ½ page*

Gallstone disease affects over 20 million Americans. Among patients with gallbladder disease, the prevalence of choledocholithiasis (stones in the bile duct) is estimated to be 10-20%. Endoscopic retrograde cholangiopancreatography (ERCP) is considered the standard of care for removing stones in the bile duct utilizing a variety of conventional methods including biliary sphincterotomy, sphincteroplasty, extraction balloon, retrieval basket, and mechanical lithotripsy. After removal of stones from the bile duct, an occlusion cholangiogram is usually performed to confirm complete bile duct clearance. However, cholangiogram can miss residual stones in 11- 30% of cases - especially in the setting of a dilated bile duct, large stones, severe pneumobilia, juxtapapillary diverticulum, primary sclerosing cholangitis, and after lithotripsy (mechanical, electrohydraulic, or laser). The approach to patients with choledocholithiasis requires careful attention because missed bile duct stones can cause recurrent biliary symptoms, pancreatitis, cholangitis, and has significant cost implication with the need for repeat imaging and/or procedures.

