### **Exclusion criteria**

1. Patients less than 18 years of age.
2. Patients not undergoing ERCP as their standard of care.
3. Patients who had the following surgeries - Billroth II surgery, Roux-en-Y Gastric bypass surgery, and Whipple's surgery.

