## 8. NUMBER OF SUBJECTS

- *Indicate the total number of subjects to be accrued locally. If applicable, distinguish between the number of subjects who are expected to be pre-screened, enrolled (consent obtained), randomized and complete the research procedures.*
- *If your study includes different cohorts, include the total number of subjects in each cohort.*
- *If this is multisite study, include total number of subjects across all sites.*

Number of patients: 100 who undergo POC in NSUH and in LIJMC

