### **Secondary Endpoints:**

- b. Identify the change in management after finding stone on POC e.g. balloon sweep, stent placement, etc.
- c. Identify the recurrence of biliary obstructive symptoms and/or imaging suggestive of recurrent (missed) stones which will be assessed with phone call at 3 months after procedure.

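### The 3-month recurrence proportion pools subjects with and without a gallbladder, so as planned it cannot separate stones left behind from new ones and should not be labelled as missed stones

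*Combined protocol and SAP*

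**What the plan says.** The 3-month outcome appears in four places.

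- **Secondary Endpoints (Section 4, repeated in Section 10)** cover recurrent obstructive symptoms and/or "imaging suggestive of recurrent (missed) stones which will be assessed with phone call at 3 months after procedure".
- **Research procedures (Section 11), item 4** has the follow-up contact made "to document any recurrent stones/procedures/interventions". No item records whether a stone is judged residual or new.
- **Endpoint Variables (Section 12), item 3** defines the variable as "Recurrent stones within 3 months after POC, and documentation of cholecystectomy as applicable".
- **Statistical Methods (Section 12), item 3** gives the analysis: "The proportion of subjects with recurrent stones will be estimated, along with the associated exact 95% binomial confidence interval". Cholecystectomy is not mentioned in any of the three methods.

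Endpoint Variables item 1 defines missed stones separately, through cholangioscopy alone: "Patients will be considered to have missed stones on conventional ERCP, if, after ERCP, one or more stones are seen with POC".

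On eligibility (Section 7), the only surgical exclusions are "Billroth II surgery, Roux-en-Y Gastric bypass surgery, and Whipple's surgery". Prior cholecystectomy is neither required nor excluded.

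**The concern.** The background in Section 2 places duct stones in the setting of gallbladder disease: "Among patients with gallbladder disease, the prevalence of choledocholithiasis (stones in the bile duct) is estimated to be 10-20" percent. A subject who leaves the procedure with a gallbladder in place therefore has a possible source of new duct stones during the next 3 months. A stone found in that window may have been overlooked by both ERCP and cholangioscopy, or it may have arrived afterwards. The bracketed word in the endpoint description assumes the first, and nothing in the plan distinguishes the two.

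This affects what the follow-up result can support. The primary endpoint counts what cholangioscopy sees after ERCP. It does not show what remains once both are finished. The 3-month outcome is the only planned observation bearing on that, and Section 4 gives confirmation of complete stone extraction as a reason for using cholangioscopy. New stones can only raise the pooled proportion. The rise depends on how many subjects keep their gallbladder and for how long.

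**Working it through.** **1. The plan's own figures.** The Sample Size Justification tabulates exact 95% intervals for the primary endpoint at n = 100 (Section 8: "Number of patients: 100 who undergo POC in NSUH and in LIJMC"). With x events, the lower limit is the 0.025 quantile of Beta(x, n − x + 1) and the upper limit is the 0.975 quantile of Beta(x + 1, n − x).

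| x/n | Plan | Recomputed |
|---|---|---|
| 10/100 | 4.9% to 17.6% | 4.90% to 17.62% |
| 20/100 | 12.7% to 29.2% | 12.67% to 29.18% |
| 30/100 | 21.2% to 40.0% | 21.24% to 39.98% |

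All three reproduce. The plan states no figure for 3-month recurrence, so no stated number is in dispute.

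**2. The text side by side.**

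- Endpoint description (Sections 4 and 10): recurrence is glossed as missed.
- Variable definition (Section 12): recurrence is paired with cholecystectomy, so the plan foresees that gallbladder status can differ or change.
- Analysis (Section 12): one pooled proportion, with no use of cholecystectomy.
- Eligibility (Section 7): gallbladder status is unrestricted.

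No section gives a rule for telling a residual stone from a new one.

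**3. How much mixing is possible.** Three quantities are needed and the documents give none of them. All are assumptions:

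- g, the share of subjects with a gallbladder in place: 20% to 80%
- m, the probability of a recurrence due to a stone left behind: 2% to 5%
- w, the probability of a new duct stone within 3 months when the gallbladder is in place: 2% to 10%

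Counting each subject once and treating the two sources as independent:

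- pooled proportion = m + g × w × (1 − m)
- share of counted cases that are new = g × w × (1 − m) / pooled proportion

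| g | m | w | Pooled proportion | Share new |
|---|---|---|---|---|
| 20% | 2% | 2% | 0.02 + 0.20 × 0.02 × 0.98 = 2.4% | 16% |
| 20% | 5% | 2% | 0.05 + 0.20 × 0.02 × 0.95 = 5.4% | 7% |
| 50% | 5% | 5% | 0.05 + 0.50 × 0.05 × 0.95 = 7.4% | 32% |
| 80% | 2% | 10% | 0.02 + 0.80 × 0.10 × 0.98 = 9.8% | 80% |
| 80% | 5% | 10% | 0.05 + 0.80 × 0.10 × 0.95 = 12.6% | 60% |

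Over the whole grid the pooled proportion runs from 2.4% to 12.6%, and the share of new stones from 7% to 80%.

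**4. What a split would show.** As a hypothetical, a pooled 10/100 = 10% (4.9% to 17.6%) could consist of 2/50 = 4% (0.5% to 13.7%) without a gallbladder and 8/50 = 16% (7.2% to 29.1%) with one. The pooled figure cannot reveal this. The stratum intervals are wide and support description only.

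**The case against.** The strongest reply is that the statistical section never calls a 3-month recurrence a missed stone. Missed stones are defined by cholangioscopy and analysed under Method 1; recurrent stones are a separate variable analysed under Method 3. A reader might infer that new stones are counted into the missed-stone result. They are not: that result is fixed at the index procedure. This part of the reply stands. The labelling problem lies in the endpoint description, not in Method 3.

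Second, recurrence is not among the two Specific Aims in Section 12, no test or decision depends on it, and the pooled proportion is a sound description of recurrence from any cause. This also stands and limits the weight of the point.

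Third, a reader might infer that many subjects keep a stone-bearing gallbladder. The documents do not show this. The Section 2 prevalence figure concerns duct stones among patients with gallbladder disease, not gallbladder status in this cohort, and the inclusion criteria select a particular group whose surgical history is unknown. Only the weaker statement follows: some subjects may have a gallbladder in place.

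Fourth, at n = 100 the distortion may be no larger than sampling error: 2/100 gives 0.2% to 7.0% and 5/100 gives 1.6% to 11.3%, and these overlap heavily. That is true, but the reported interval conveys sampling error and does not convey the mixing.

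Last, medical history, procedures and cholecystectomy are already collected, so a split could perhaps be made afterwards. It is not planned, however, and neither baseline gallbladder status nor the date of surgery is a named data item.

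**Conclusion.** The point holds in a limited form. As planned, the 3-month proportion cannot separate stones left behind from new stones arising from a gallbladder in place, so it should not be read as a missed-stone rate. It remains valid as all-cause 3-month recurrence, and the primary endpoint is unaffected.

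It would go too far to say that the endpoint is invalid or that its bias is known to be large. The 7% to 80% range rests entirely on assumed values of g, m and w; the documents fix none of them. That some subjects have a gallbladder is inferred from the absence of any restriction at entry and from the provision to document cholecystectomy where applicable.

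This is an inexpensive improvement to a descriptive secondary endpoint.

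**What to change.** 1. Remove the bracketed *missed* from the secondary endpoint in Sections 4 and 10.
2. Keep the pooled proportion in Method 3, labelled as 3-month recurrence from any cause.
3. Add gallbladder status at the index ERCP (absent or in place) and the date of any later cholecystectomy to the case report form.
4. Amend Method 3 to also report recurrence, with exact 95% intervals, by baseline gallbladder status. Describe the gallbladder-absent group as the estimate least affected by new stones. It is not a pure missed-stone rate, because lack of a gallbladder rules out migration from it but not every new duct stone.
5. List the timing of any cholecystectomy relative to recurrence descriptively. Do not form analysis groups by surgery after baseline, since whether and when it happens may depend on recurrence.

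The cost is two data items and a few lines of analysis text, with no extra subjects or procedures. The drawback is the wide subgroup intervals, so the split should be presented as descriptive.

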#### 4. OBJECTIVE(S)/SPECIFIC AIMS AND HYPOTHESES

- *A concise statement of the goal(s) of the current study.*
- *The rationale for and specific objectives of the study.*
- *The goals and the hypothesis to be tested should be stated.*

This is Prospective, single center study (One IRB, Two hospitals: North Shore University Hospital [NSUH] and Long-Island Jewish Medical Center [LIJ])

The primary goal of the study is to assess if POC will enhance the diagnostic yield in the detection of residual biliary stones that are missed during conventional ERCP. Residual bile duct stones can especially be seen in the setting of bile duct dilation, history of recurrent abnormal liver function tests, and after lithotripsy (mechanical, electrohydraulic, or laser). Missed biliary stones can lead to recurrent biliary symptoms, pancreatitis, and cholangitis. POC after conventional ERCP can be a useful diagnostic tool to confirm complete extraction of bile duct stones, and thus lead to decreased morbidity and decreased cost by avoiding unnecessary tests and repeat procedures.

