#### Primary Endpoint:

The primary end point is to detect the presence of any stones seen during POC that were missed during conventional ERCP

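### The planned 3-month recurrence proportion pools clear-POC and stone-positive subjects, so it does not show how often a clear POC is followed by a stone

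*Combined protocol and SAP*

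**What the plan says.** Section 4 gives the rationale: "POC after conventional ERCP can be a useful diagnostic tool to confirm complete extraction of bile duct stones". Section 12, Specific Aims, item 1 is worded as "To estimate the proportion of subjects with missed stones on conventional ERCP". Endpoint Variables, item 1 defines the term by what POC shows: "Patients will be considered to have missed stones on conventional ERCP, if, after ERCP, one or more stones are seen with POC". The primary endpoint in Sections 4 and 10 is likewise framed by what is visible: "The primary end point is to detect the presence of any stones seen during POC that were missed during conventional ERCP".

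For follow-up, the secondary endpoint in Section 10 covers symptoms and "imaging suggestive of recurrent (missed) stones which will be assessed with phone call at 3 months after procedure". Section 11, Research procedures, item 4 applies the 3-month contact to every enrolled subject in whom cholangioscopy was done, whatever it showed. Item 1 of the same list records the POC result: "Document the number of subjects who did and did not have any missed stones as identified by SpyGlass".

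The recurrence analysis is Statistical Methods, item 3: "The proportion of subjects with recurrent stones will be estimated, along with the associated exact 95% binomial confidence interval". It names no subgroup. Item 2, on change in management, does: "This analysis will be restricted to subjects with missed stones".

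**The concern.** A later stone means different things in the two groups. After a clear POC, it raises the possibility that POC missed it as well as ERCP. After a positive POC, the subject has had further treatment, so a later stone may reflect incomplete treatment, another stone that POC did not show, or a new stone. One proportion over both groups answers neither question.

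At stake is whether the report addresses the reason given for using POC. If the plan is followed as written, the report will not state how often a clear POC was followed by a stone. A split made after the results are known would carry less weight than one specified now.

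A related point of interpretation concerns the primary. A subject with a clear POC and a stone at 3 months counts as having no missed stone in the primary, while the secondary endpoint's parenthesis describes such stones as missed. The plan does not say how the primary proportion relates to the full ERCP miss rate, which is how aim 1 can be read.

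**Working it through.** **Inputs from the documents.** 100 subjects with POC (Section 8); an expected 11% to 30% with a stone on POC, with a table at 10%, 20% and 30% (Section 12, Sample Size Justification); exact two-sided 95% binomial intervals. The documents give no recurrence rate and no sensitivity or false-positive rate for POC. Values for these below are assumptions. All 100 subjects are taken as reached at 3 months.

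**1. Reproduce the plan's table.** The Clopper-Pearson lower limit is the 2.5% quantile of Beta(x, n-x+1), and the upper limit is the 97.5% quantile of Beta(x+1, n-x). With n = 100:

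- x = 10: 4.90-17.62%
- x = 20: 12.67-29.18%
- x = 30: 21.24-39.98%

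All three agree with the plan.

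**2. What pooling hides.** With 20 POC-positive subjects, the pooled rate = 0.8 × clear-POC rate + 0.2 × POC-positive rate. Assume 5 recurrences in total. The pooled result is always 5/100 = 5.0% (1.6-11.3%).

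| Recurrences, clear POC (n = 80) | Rate (95% CI) | Recurrences, POC-positive (n = 20) | Rate (95% CI) |
|---|---|---|---|
| 5 | 6.25% (2.1-14.0%) | 0 | 0% (0-16.8%) |
| 4 | 5.0% (1.4-12.3%) | 1 | 5.0% (0.1-24.9%) |
| 2 | 2.5% (0.3-8.7%) | 3 | 15.0% (3.2-37.9%) |
| 0 | 0% (0-4.5%) | 5 | 25.0% (8.7-49.1%) |

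The ambiguity is lopsided. The clear-POC rate cannot exceed the pooled rate divided by 0.8 (5.0% / 0.8 = 6.25%), but it can be as low as zero.

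**3. Precision after the split.** At 10%, 20% and 30% POC-positive, the clear-POC group has 90, 80 and 70 subjects. With zero events the upper limit is 1 - 0.025^(1/n).

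- Clear POC, 0 events: 4.0%, 4.5%, 5.1%
- Clear POC, 2 events: 0.3-7.8%, 0.3-8.7%, 0.3-9.9%
- POC-positive (n = 10, 20, 30), 0 events: 30.8%, 16.8%, 11.6%

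**4. Added yield against ERCP miss rate.** If every stone seen on POC is real, the true residual-stone rate = seen rate / sensitivity. Take 20% seen:

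| Assumed POC sensitivity | True residual-stone rate | Clear-POC subjects with a retained stone, (true - 0.20)/0.80 |
|---|---|---|
| 95% | 21.1% | 1.3% |
| 90% | 22.2% | 2.8% |
| 80% | 25.0% | 6.25% |
| 70% | 28.6% | 10.7% |

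The seen rate is then a lower bound. The condition matters. With a true rate of 25%, sensitivity 90% and a 5% false-positive rate, POC positivity is 0.25 × 0.90 + 0.75 × 0.05 = 0.225 + 0.0375 = 26.25%, which is above the true rate.

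**The case against.** The strongest reply has four parts.

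- **The data exist.** A reader might infer that the trial cannot show what follows a clear POC. The documents do not support that: the POC result and the 3-month outcome are both recorded for each POC subject, and nothing forbids a split. What stands is that the split is not planned.
- **The primary is added yield.** A reader might also infer that the primary assumes POC sees every stone. No such assumption is stated. The endpoint and its definition rest on stones seen with POC, and the sample-size table is headed the same way. On that reading, a clear-POC subject with a later stone is not misclassified, because the primary describes the index procedure. Only the short wording of aim 1 invites the wider reading.
- **Clearance is rationale, not an aim.** Neither of the two aims in Section 12 concerns recurrence after a clear POC, and recurrence is a descriptive secondary endpoint. This limits the severity. It does not make the pooled figure informative on the stated rationale.
- **The split is not a clean test.** Outcome is obtained by phone with no scheduled imaging, so silent stones go unseen. Retained and newly formed stones cannot be separated; cholecystectomy is documented but not used in the analysis. Recurrence after a positive POC need not be treatment failure alone. Clear-POC subjects make up most of the pool, and intervals for different splits overlap. All of this stands, and it is why the result should be called a partial check.

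**Conclusion.** The point holds as a gap in the planned analysis. Item 3 yields one recurrence proportion over two groups that answer different questions, and the clear-POC proportion that bears on the Section 4 rationale is not reported. In the illustration, a pooled 5.0% is compatible with clear-POC rates from 0% to 6.25%. That range depends on the assumed 5 events and 20 POC-positive subjects, and on complete follow-up.

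The primary calculation and the sample-size table are correct and unaffected. The primary is sound as added yield. It is a lower bound on the ERCP miss rate only if stones seen on POC are real, and the size of any shortfall depends on a sensitivity that the documents do not give. It would be too strong to say that nothing checks POC: follow-up of clear-POC subjects does so in part, once it is reported separately. The change is worth making but is not critical.

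**What to change.** **Statistical Methods, item 3.** Report recurrent stones separately for POC-negative and POC-positive subjects, each with an exact 95% interval. Name the POC-negative proportion as the one bearing on clearance, and keep the pooled proportion as descriptive. State that follow-up is by phone without scheduled imaging and cannot separate retained from newly formed stones, so the result is a partial check on POC.

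**Statistical Methods, item 1.** Describe the primary as the added yield of POC after ERCP, and say that it is a lower bound on the ERCP miss rate only if stones seen on POC are real. Label as exploratory any estimate that also counts POC-negative subjects with a stone within 3 months as missed. As an illustration, 4 such subjects would move 20/100 (20.0%, 12.7-29.2%) to 24/100 (24.0%, 16.0-33.6%).

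**Cost.** A few lines in Section 12, with no new data, visits or subjects. The price is a wide interval in the small POC-positive group.
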